 - Lactation, pregnancy, or intending to become pregnant during the course of the study.
 - Alcohol use in the past 7 days.
 - Illicit substance use in past 7 days (e.g., heroin, methamphetamines).
 - Under a conservatorship.

Aim 2: Methadone group (n=10):

- **Inclusion criteria for methadone group includes:**
 - Age 18-65.
 - A prescription for liquid methadone at dose \geq 60mg.
 - Taken methadone as prescribed in the last 7 days.
- **Exclusion criteria for methadone group includes:**
 - Age <18 or >65.
 - A condition preventing or complicating ISF collection. Conditions may include dermatological (skin) condition, immunodeficiency, recent blood donation, anemia, cancer, congestive heart failure, HIV, HCV, or TB. Any active severe depression (e.g., suicidal ideation) or mania symptoms.
 - Lactation, pregnancy, or intending to become pregnant during the course of the study.
 - Alcohol use in the past 7 days.
 - Illicit substance use in past 7 days (e.g., heroin, methamphetamines).
 - Under a conservatorship.

Aim 3: Establish correspondence between ISF & Blood (n=22):

- **Inclusion criteria for this group includes:**
 - Age 18-65.
 - A prescription for buprenorphine at dose \geq 16 mg/4mg, a prescription for buprenorphine/naloxone at dose \geq 16 mg/4mg, a prescription for methadone at dose \geq 60mg, or part of the control group.
 - Taken buprenorphine, buprenorphine/naloxone, or methadone as prescribed in the last 7 days, or part of the control group.

- **Exclusion criteria for this group includes:**

- Age <18 or >65.
- A condition preventing or complicating ISF collection. Conditions may include schizophrenia, bipolar, depression, dermatological (skin) condition, immunodeficiency, recent blood donation, anemia, cancer, congestive heart failure, HIV, HCV, or TB.
- Any active severe depression (e.g., suicidal ideation) or mania symptoms.
- Lactation, pregnancy, or intending to become pregnant during the course of the study.
- Alcohol use in the past 7 days.
- Illicit substance use in past 7 days (e.g., heroin, methamphetamines).
- Under a conservatorship.

Control Group (n=2):

- **Inclusion criteria for control group includes:**

- Age 18-65.

- **Exclusion criteria for control group includes:**

- Age <18 or >65
- Prescription for opioid medications (e.g., buprenorphine, buprenorphine/naloxone, methadone)
- Have not taken any opioids agonist medications (e.g., buprenorphine, buprenorphine/naloxone, methadone) in the last 7 days.

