Subject Recruitment Strategy: Up to 18 adults ages 18-65 years of age will be recruited to participate in this study. Subjects will be recruited from addiction medicine clinics through provider referrals (e.g., El Dorado Community Service Centers). Human subjects research will be performed at Synergy Research Centers (<https://www.synergyresearchcenters.com>) in San Diego which is a well-established clinical trial company that provides appropriate staff and facilities to conduct this study.

Study Procedures: The study consists of a 1) pre-screening phone call, 2) online assessment, 3) an in-person baseline clinical visit which will include a urine toxicology test, urine pregnancy test, pre blood sample, ISF extractions, and post blood sample, and 4) a post-ISF extraction follow-up call approximately 2 days after baseline visit. As such, there will only be one in-person visit.

- **Screening (up to 10 minutes)**

- Potentially eligible subjects will be identified by the research team and clinical staff through addiction medicine clinic referrals. The screening process may occur in-person or online. However, subjects will use an online screening process in both situations.
- Study eligibility will be conducted by the clinical research coordinator (CRC). See the supplemental material for specific questions.

- **Consent (up to 10-30 minutes):**

- If the potential subjects meet the inclusion criteria, does not meet the exclusion criteria, and agrees to learn more about the study, the CRC will send the study consent document link via an online Good Clinical Practice (GCP) compliant program to the subject for review.
- The CRC will walk the subjects through the consent and answer any questions the subject might have. As such, there will be no paper consents.

- **Initial questionnaire (up to 15-30 minutes):**

- If the potential subjects agree to participate as indicated by their online signature on the consent, they will be assigned a computer-generated Subject ID code and will be asked to complete the online baseline questionnaire in a GCP compliant data collection program (see the supplemental material for specific questions).
 - Demographics (e.g., age, sex, race, ethnicity)
 - Past and current diseases or medical conditions
 - Previous operations or medical procedures
 - Any medicines, vitamins, minerals, and herbal remedies that the person is currently taking
 - Diet and exercise habits
 - Tobacco, alcohol and other substance use history

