 - Previous pregnancy history (if female)
- The questionnaire will include the following:
 - Demographics (e.g., age, sex, race, ethnicity)
 - Past and current diseases or medical conditions
 - Previous operations or medical procedures
 - Any medicines, vitamins, minerals, and herbal remedies that the person is currently taking
 - Diet and exercise habits
 - Tobacco, alcohol and other substance use history
 - Previous pregnancy history (if female)
- The CRC will schedule an in-person clinical visit for the subjects if needed. Subjects will be instructed to take their medications as prescribed by their physician (e.g., dose, dosing times). As

such, the in-person visits will be scheduled around the subjects usual dosing time. For the control group, in-person assessments may occur at any time during the available clinic hours. Subjects will also be asked to abstain from alcohol and non-prescribed substances at least 24 hours before their in-person assessment.

- **In-person study visit within 7 days after the consent and online assessment is completed:**

- a. Physical assessment (up to 30 minutes)**

- i. The in-person assessment may include the following:
 1. Limited physical exam:
 - a. Height and weight measurements
 - b. Feeling for the pulse
 - c. Listening to the heart and lungs with a stethoscope
 - d. Measuring blood pressure using a sphygmomanometer
 2. Changes in medications in the past week
 3. Use of substances (e.g., opioids, alcohol) in the past week
 4. Urine toxicology test which will test for the following substances: barbiturates, benzodiazepines, amphetamine, methamphetamines, cocaine, heroin, oxycodone, or other opiates. Subjects will be discharged from the study if they test positive for any of the listed non-prescribed medications tested and they will be paid a total of \$50.
 5. Urine pregnancy test for premenopausal women. Subjects to be discharged if they test positive, paid \$50, and referred to their primary care doctor or OBGYN.

- b. First blood sample collection (up to 10 minutes)**

Immediately before the patient takes their prescribed medication, a standard venipuncture blood sample will be collected by a certified clinician. This sample will be used for comparative analysis with the ISF sample. For those in the control group, this will occur immediately after the physical assessment is completed.

- c. First Microneedle ISF collection (up to 1 hour)**

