- i. A second ISF collection will occur at the medication peak (e.g., 2-4 hours after medication administration). The ISF collection process described previously will be employed.

f. Second blood sample collection (10 minutes)

- i. After the second ISF collection, a standard venipuncture blood sample will be collected by a certified clinician. This sample will be used for comparative analysis with the ISF samples.

• Method of sample preservation

- a. Blood samples will be centrifuged and kept in the refrigerator.
- b. ISF samples will be stored at -80C and transported to the laboratory in a dry ice container.
- c. All samples will be transported to the laboratory within 24 hours of collection.

• Follow-up call/visit (15 minutes)

- a. Approximately 2 days after ISF collection, subjects will be contacted by the CRC via phone. Subjects will be asked to report their tolerability, pain, and experience. Their responses will be documented in a secure an online storage medium.

• Compensation: Subjects will be compensated with an online visa gift card worth up to \$250 for their participation in this study. Participants will be compensated \$25 for the initial online assessment (up to 15-30 minutes), \$30 for the in-person physical exam and data collection (up to 30 minutes), \$10 for the first pre ISF collection blood (up to 10 minutes), \$150 for two ISF collection and monitoring (2 collections up to 60 minutes each [\$75 each]), \$10 for the post ISF collection blood collection (up to 10 minutes each), and \$25 for the follow-up call (up to 15 minutes).

All the biological samples collected in this study (e.g., ISF, blood; about 2ml per sample) will be tested for the subject's prescribed medications and their metabolites at a laboratory that has experience with these types of samples (e.g., Expert Chemical Analysis (*ECA*); <http://ecalab.com/>). Urine will be tested for illicit substances to inform eligibility.

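### The eligibility urine panel names neither buprenorphine nor methadone, so an undisclosed user could be sampled as one of the two drug-free controls

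*Protocol*

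**What the plan says.** Protocol, STUDY DESIGN / METHODS / PROCEDURES, A. Summary of the Research Design, a. Physical assessment, item 4, sets out the panel: "Urine toxicology test which will test for the following substances: barbiturates, benzodiazepines, amphetamine, methamphetamines, cocaine, heroin, oxycodone, or other opiates". The consequence comes next: "Subjects will be discharged from the study if they test positive for any of the listed non-prescribed medications tested". After the compensation paragraph, the paragraph on biological samples gives the purpose: "Urine will be tested for illicit substances to inform eligibility".

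Under PARTICIPANT SELECTION, Control Group (n=2), the first drug-related exclusion is "Prescription for opioid medications (e.g., buprenorphine, buprenorphine/naloxone, methadone". The next item concerns opioid agonist use in the preceding 7 days and again names both study drugs.

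On the source of participants, the Subject Recruitment Strategy says: "Subjects will be recruited from addiction medicine clinics through provider referrals". No separate source is given for controls.

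**The concern.** The study asks whether buprenorphine, methadone and their metabolites can be detected in ISF. The controls are its only drug-negative reference: they show what the collection and assay return when no drug should be present. That works only if they are in fact unexposed.

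The eligibility criteria name the two drugs when they define a control. The laboratory test that could verify this at the visit does not name them. If someone with undisclosed use is sampled as a control, a true positive could be read as background or carry-over. If the exposure is recognised later, that control is lost after the only visit.

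**Working it through.** The point rests mainly on a comparison of sections. The Protocol gives no figure of its own to reproduce.

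**Step 1: the panel against the control definition.** Item 4 has seven named entries (barbiturates, benzodiazepines, amphetamine, methamphetamines, cocaine, heroin, oxycodone) and one catch-all. Of the two study drugs, 0 of 2 are named. The control exclusions name both. The discharge rule is tied to substances that are listed, so whether a buprenorphine or methadone positive leads to discharge depends on how the catch-all is read. The stated purpose of testing for illicit substances does not settle this, because both drugs are prescribed medicines in this study.

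**Step 2: what else would stop an exposed control before sampling.**
- Clinic referral and identification of candidates by clinical staff. This is not self-report, but it is not a test of exposure either.
- The screening questions and the online questionnaire on current medicines and substance use. These are self-report.
- The visit items on medication changes and past-week substance use, including opioids. These are also self-report.
- The 7-day item in the control exclusions. It is worded in the negative, so as an exclusion it literally removes people who have not taken opioid agonists. The intent is clear, but the text says the opposite.

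None of these is designed to find use that the person does not disclose.

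**Step 3: what would show exposure after sampling.** Blood is drawn alongside both ISF collections, and B. Analysis of Study Results covers samples from up to all 22 participants. Blood could therefore reveal an exposed control, but only after the one in-person visit. The paragraph on biological samples limits testing to each participant's own prescribed drug and its metabolites. A control has no such prescription, so read literally that sentence names no analyte for a control.

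**Step 4: size, given one exposed control.**
- Share of the control group: 1/2 = 50%.
- Planned control samples: 2 people x 2 collection times x 2 fluids = 8.
- Samples from one control: 2 times x 2 fluids = 4, so 4/8 = 50%.

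These figures are conditional. The Protocol gives no basis for the probability that a control is exposed, and none is assumed here.

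**The case against.** The strongest reply is that this is an exploratory pilot with paired blood. An exposed control would probably show drug or metabolite in blood at both times, so the corruption would not be hidden. The catch-all may also be meant to include both drugs. Much of this stands: the harm is more likely a control lost after sampling than an error nobody can find, and the panel is ambiguous rather than shown to omit the drugs. It does not remove the point. Blood results come too late to keep the person out, the literal assay scope leaves controls without an analyte, and a test that decides eligibility should not leave the study drugs to interpretation.

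A reader might infer more than the documents support:
- **That this panel is the only laboratory eligibility check.** It is not; the same list includes "Urine pregnancy test for premenopausal women", and a positive result there also leads to discharge. The panel is the only laboratory check of drug exposure.
- **That everything rests on an online screen.** Referral, clinical-staff identification and in-person questions also contribute.
- **That an opiate screen would miss these drugs.** The Protocol gives no assay type or specificity, so this cannot be argued from it.
- **That a patient taking the other study drug breaks a criterion.** No patient criterion excludes the other drug by name; only the illicit-use exclusion could apply.
- **That a non-adherent patient would count against ISF detection.** Patients take a dose on site before the second collection, and a negative ISF result beside a negative blood result says nothing against ISF. Nor could one urine result establish "Taken methadone as prescribed in the last 7 days".

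**Conclusion.** The point holds for the control group only. The one laboratory drug test used for eligibility does not clearly cover the two drugs whose absence defines a control, and what remains before sampling is referral and self-report among people recruited from addiction medicine clinics.

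If one control is exposed, half the negative reference is affected. This rests on three readings: that the catch-all for other opiates is not already specified elsewhere to include both drugs, that controls come from the stated recruitment source because no other is given, and that the urine test is run on everyone. On the last, the Study Procedures summary says the visit will include it, although the list of assessments is introduced permissively.

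The likelihood of the event is unknown, and the study is exploratory. The correction is worth making because it is cheap and acts before sampling, not because the study fails without it.

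**What to change.** 1. In a. Physical assessment, item 4, name buprenorphine and methadone (or its metabolite EDDP) on the panel. State that the existing discharge rule for non-prescribed positives applies to controls before any blood or ISF is taken. Make clear that a patient's own prescribed drug is not a non-prescribed positive.
2. In the paragraph on biological samples, state that control blood and ISF are assayed for all study analytes: buprenorphine, norbuprenorphine, B3G, methadone and EDDP.
3. In the Control Group exclusions, reconcile the 7-day opioid agonist item with the definition of a control, since its present wording reverses it.

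The panel change costs two more analytes on urine already collected, with no new visit or sample. It may produce an extra discharge, paid at $50 under the existing rule. That control would then need replacing to keep n=2, and the Protocol states no replacement rule. The other two items are wording changes; item 2 adds assay work only if control samples were not already to be tested for all five analytes.

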Aim 3: Establish correspondence between detected medication levels in ISF and blood. Medication levels for buprenorphine and methadone detected in the ISF will be compared to medication levels measured in blood samples for the purpose of understanding the correlation between the ISF and blood levels.

C. Background of the Study

Substance misuse is an immense problem for our society today, with heavy costs due to lost work productivity, health care needs, and judicial system expenses, as well as significant human costs in terms of lost lives, broken families, and unfulfilled personal potential. Substance use disorders (SUDs) are estimated to cause over \$400 billion worth of monetary damage to the US economy on an annual basis.¹ The number of deaths related to drug overdose has more than quadrupled over the last decade from approximately 16,000 in 2006 to more than 70,000 in 2019, of which 36,359 were from an opioid overdose.² An opioid use disorder (OUD) is typically a chronic, relapsing illness, associated with significantly increased rates of morbidity and mortality. With the rising overdose deaths and more than 3 million US citizens and more than 16 million citizens worldwide suffering from OUD, opioid overdose was declared a national emergency in the United States in 2017.³

Current treatment strategies are not keeping pace with the growing opioid crisis, and new solutions are urgently needed, particularly given the high relapse rates in those with an OUD.⁴ Patients who have a previous history of

overdose,⁵ who have been recently discharged from detoxification programs,⁶ or who are initiating or ending opioid maintenance therapy⁷ tend to be at a high risk of an opioid overdose.

Buprenorphine (i.e., Suboxone[®], Subutex[®]) and methadone are two medications that have been approved to treat OUD by the US Food and Drug Administration and have demonstrated the greatest opportunity for expanding access to patients in need.⁸ Improvements in prescribing medications for opioid use disorders (MOUDs), through clinical practice guidelines and continuous monitoring could ensure safer, more effective treatment options for patients while reducing opioid misuse, overdose, and death.

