- i. ISF will be collected by a board-certified physician with procedural skills, training, and familiarity with ISF collection. ISF collection will follow collection practices as described below and applied elsewhere.¹⁰ The first ISF collection will occur immediately before the participant takes their prescribed medication. A subsequent collection will occur at the medication peak (e.g., 2-4 hours after medication administration; see below).
 - ii. ISF will be collected from the surface of the right or left arm (subject preference).
 - iii. The subject will be prepared for the ISF collections using standard clean working techniques (e.g., prepped and draped).
 - iv. The procedures will involve covering the skin with a transparent film skin dressing (e.g., Tegaderm) containing a 1-cm-diameter opening where microneedle treatment will be performed.
 - v. A minimally invasive microneedle array will be used in conjunction with a standard vacuum pump. Microneedles (without the patch) will be inserted and removed multiple times (~10) to collect about $\geq 1 \mu\text{l}$ of ISF. This approach has been well tolerated with faint visual evidence of micropores in the skin in a previous study.¹⁰ A standard vacuum pump will then be administered at -50 kPa at room temperature for 20 min to draw out the ISF. Skin appearance should remain largely unchanged and result in a swift recovery as seen in a previous study.¹⁰ Commercially available gauze will then be used to collect the ISF from the surface of the skin.

- vi. After the ISF collection is complete, a sterile bandage covering will be supplied to the area.
- vii. Subjects will be monitored after each ISF collection for up to 30 minutes and be asked to report their tolerability, pain, and experience. Their responses will be documented in a secure GCP certified online storage medium.
- viii. This process will also occur for the control group. Because the control group will not be administered a medication, the timing of the blood and ISF collection will occur after physical assessment and 2-4 hours after the first collection.

d. Prescribed dose of medication (5 minutes)

- i. Participants will be asked to take their prescribed oral medication at the study site. Study personnel may observe.

e. Second Microneedle ISF collection (up to 1 hour)

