The unique Subject ID code will be used to link all data in an individual file because such linkage is critical for communication with the subject. Research data will be separated from identifying data. All data will be stored on secure servers using password protection. Data from this study will be transferred from the secure online service electronically, and stored on secure servers. All bio-samples will be labeled with the subject's ID number. As such, no identifying information will be listed on the bio-samples. All computers and files containing confidential information will be password protected and monitored by study staff. The data will be limited to a small number of project investigators and research staff. Backups of electronic data stored in a secure cloud-based location will be maintained at all times.

RISK/BENEFIT ASSESSMENT

A. Risks

The most important risks or discomforts that subjects may expect from taking part in this research include mild allergic reaction to adhesives, bleeding, bruising, infection, pain or discomfort, scarring or skin discoloration, skin inflammation, thinning, discoloration and/or redness. Although unlikely, hospitalization due to infection is possible. Based on clinical studies and post market data available for a similar approach, it is expected that the occurrence of any adverse events will be low.

As with most research involving human subject, loss of confidentiality or breach of privacy is a risk. The proposed study involves data collected over the internet and in person. Data will be transferred to and from the online data system electronically, and stored on secure servers through Synergy Research Centers.

B. Prevention of Risks

Only board-certified physicians with procedural skills and training and familiarity with ISF collection will collect the ISF. Study staff will monitor subjects for any adverse events described in the next section. The CRA will also contact the subjects two days after the procedure to assess their tolerability, pain, and experience. All potential adverse events will be assessed and reported when necessary.

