As mentioned, risks associated with confidentiality will be minimized by collecting and storing data securely. There will be no paper data (e.g., test forms) stored in locked filing cabinets/offices. A unique subject code will be created in analytic databases, as mentioned. The unique Subject ID code will be used to link all data in an individual file because such linkage is critical for data analyses. Research data will be separated from identifying data. All data will be stored on secure servers using password protection. Data from this study will be transferred from the secure online service electronically, and stored on secure servers. All computers and files containing confidential information will be password protected and monitored by study staff. As such, the data will be limited to a small number of project investigators and research staff. Backups of electronic data stored in a secure cloud-based location will be maintained at all times.

C. Adverse Events

Below is a list of the potential adverse effects (e.g., complications) associated participating in this study:

- Mild allergic reaction to adhesives
- Mild bleeding
- Mild bruising
- Mild or moderated infection
- Mild or moderate pain or discomfort
- Mild scarring or skin discoloration
- Mild skin inflammation, thinning, discoloration and/or redness.

- Although unlikely, hospitalization due to infection is possible.

D. Benefits

Besides the financial compensation outlined in this protocol, there is no immediate personal benefit to the subjects. However, it is believed that these research efforts will lead to significantly improved responses to the growing opioid epidemic. Relevant information learned in this study will be managed with care and in a respectful manner. Strict protection over subject information to ensure confidentiality will be employed.

REFERENCES

2. Overdose Death Rates | National Institute on Drug Abuse (NIDA). Accessed April 29, 2021. <https://www.drugabuse.gov/drug-topics/trends-statistics/overdose-death-rates>

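### ISF is collected on gauze from punctured, suctioned skin with no record of visible blood, so a blood-tinged sample can count as drug detected in ISF and raise the ISF:blood ratio

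*Protocol*

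**What the plan says.** The collection procedure is in Study Design / Methods / Procedures, section A, under the first microneedle ISF collection, item v. The needles are "inserted and removed multiple times (~10) to collect about" 1 microlitre or more of ISF. Next, "A standard vacuum pump will then be administered at -50 kPa at room temperature for 20 min to draw out the ISF". Last, "Commercially available gauze will then be used to collect the ISF from the surface of the skin". The second collection repeats this process.

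Item vii of the same section has tolerability, pain and experience documented after each collection. The sample preservation section says that "ISF samples will be stored at -80C and transported to the laboratory in a dry ice container". The paragraph after the compensation details has all biological samples tested for the prescribed drug and its metabolites.

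The Risks section names "mild allergic reaction to adhesives, bleeding, bruising, infection, pain or discomfort" among the possible harms, and the Adverse Events list includes "Mild bleeding". No section asks for the gauze to be inspected, for blood to be recorded, or for a blood-tinged sample to be flagged, set aside or analysed separately.

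Aims 1 and 2 rest on detecting and quantitating drug in this fluid. Aim 3 is to "Establish correspondence between detected medication levels in ISF and blood".

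**The concern.** The study asks whether the drugs appear in ISF and how ISF levels relate to blood levels. Blood holds the same analytes. If some reaches the gauze, its drug is assayed as ISF drug. That can turn a non-detection into a detection under Aims 1 and 2, and it pulls the measured ISF:blood ratio towards 1 under Aim 3. If the true ratio is below 1, the shift is upward, which favours the method.

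The design has no internal check on this. The two controls take no study drug and may not hold an opioid prescription, so blood on their gauze adds no drug signal. The error can show only in medicated participants, where it looks like a true detection. The protocol says the results will be used to develop a sensor, so an error in this direction matters.

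The point also belongs in the protocol. A statistical analysis plan can separate blood-tinged samples only if someone noted the blood at collection.

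**Working it through.** The protocol gives no figure to reproduce here: it states no blood fraction, expected drug level, true ISF:blood ratio or assay limit. The calculations below show scale only, and their inputs are assumptions unless marked as taken from the protocol.

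**1. Volume.** The target is about 1 microlitre or more (protocol, item v). In a 1 microlitre sample, 0.1 microlitre of blood is 0.1 / 1 = 10%. Very little blood is needed to make a material fraction.

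**2. Ratio in one contaminated sample.** Let f be the blood fraction of the sample and r the true ISF:blood ratio. Assume that the contaminating blood carries drug at the level measured in the blood sample. Then

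measured ratio = f + (1 - f) × r

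The shift is f × (1 - r), which is upward whenever r is below 1. With r = 0.10 (assumed):

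| f | Calculation | Measured ratio |
|---|---|---|
| 5% | 0.05 + 0.95 × 0.10 | 0.145 |
| 10% | 0.10 + 0.90 × 0.10 | 0.19 |
| 20% | 0.20 + 0.80 × 0.10 | 0.28 |

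With r = 0, the sample reads f times the blood level. It counts as a detection if that exceeds the assay limit.

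**3. Chance that a group is touched at all.** If a proportion p of collections were blood-tinged, independently, the chance of at least one among 10 patients at one time point is 1 - (1 - p)^10. This is 40% for p = 5%, 65% for p = 10% and 89% for p = 20%. The values of p are assumed.

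**4. False ISF-blood correlation.** Suppose ISF held no drug, so that measured ISF = f × blood level. Take n = 10 (the protocol's size for each medication group), lognormal blood levels, f uniform from 2% to 10% in contaminated samples and 0 in the rest, and 4,000 simulated sets. The mean correlation is:

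| Contaminated samples | Blood CV 30% | Blood CV 50% | Blood CV 70% |
|---|---|---|---|
| 10 of 10 | 0.55 | 0.72 | 0.80 |
| 5 of 10 | 0.19 | 0.26 | 0.31 |
| 3 of 10 | 0.11 | 0.16 | 0.17 |
| 2 of 10 | 0.07 | 0.09 | 0.10 |
| 1 of 10 | about 0 | about 0 | about 0 |

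The simulation treats every level as measurable. The effect on a single sample (step 2) needs only one contaminated sample. The effect on the correlation is large only when contamination is close to universal.

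**The case against.** **Bleeding is not tied to the ISF site.** The risk lists cover the whole study, which includes two venipunctures, and the protocol expects few adverse events. For the microneedle site it expects only faint micropores and largely unchanged skin. This stands. A reader might infer that the protocol expects blood on the gauze; it says only that bleeding is possible in the study. The frequency of contamination is unknown, which is itself a reason to record it.

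**The correlation effect can be overstated.** A reader might infer that contamination alone would produce a convincing ISF-blood correlation of 0.55 to 0.80. That requires blood in all 10 samples. If contamination is occasional, the figure falls to about 0.1 to 0.2, which also stands.

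**A visual check may miss the harm modelled.** On 1 microlitre, 2% to 10% blood is 0.02 to 0.10 microlitre, which may not be visible on gauze. A clean-looking subset could then reassure wrongly. This stands as a limit on the remedy. It is not a reason to record nothing, since gross contamination would be caught.

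**A check may exist elsewhere.** Collection follows practice from a cited ISF study, the sponsor has run an earlier ISF study, and the collecting physician is to be familiar with the technique. Those sources may contain a blood check, but the protocol states none, and its own account of what is documented after collection leaves blood out.

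**The sensitivity analysis belongs in the analysis plan.** This is fair for the analysis itself, but not for the flag it depends on.

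**Conclusion.** The point holds as a gap in the collection procedure with a foreseeable direction of bias. As written, drug carried by blood on the gauze can be counted as drug detected in ISF and can raise the ISF:blood ratio, and neither the controls nor a later analysis can reveal it. For a single sample, a true ratio of 0.10 would read 0.145 to 0.28 at 5% to 20% blood. This rests on an assumed ratio, assumed blood fractions, and contaminating blood at the measured blood level. Whether such a sample crosses the assay limit cannot be judged from the protocol.

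The documents do not support the stronger inference that the answers to Aims 1 to 3 will be wrong. They show neither that contamination is frequent nor that the ISF-blood correlation would be mainly an artefact. In this exploratory pilot of 22 people, the safeguard is worth adding because it costs little and the missing information cannot be recovered afterwards.

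**What to change.** In item v of the first ISF collection, which also governs the second, add that the gauze is inspected after each collection and visible blood (yes/no) is recorded on the existing electronic data sheet. In Analysis of Study Results, or in the statistical analysis plan, state that detection rates and the ISF-blood comparison are reported both for all samples and for samples without visible blood. State as a limitation that traces too small to see remain undetected.

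The cost is one data item and one extra analysis, with no added assay or visit. The analysis of samples without visible blood will have fewer samples. How many fewer cannot be predicted, and if many are flagged, that analysis will be imprecise with groups of 10.
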